405		• Visual acuity area under the curve (AUC) between randomization and 24 weeks
406		 Mean change in OCT CSF thickness, adjusted for thickness at time of
407		randomization
408		• Percent of eyes with ≥ 1 and ≥ 2 logOCT step gain or loss in CSF thickness
409		• Percent of eyes with OCT CSF thickness (in micros) < the following gender and
410		OCT machine-specific values: <290 in women and <305 in men in Zeiss Cirrus;
411		<305 in women and <320 in men in Heidelberg Spectralis
412		 OCT CSF thickness AUC between randomization and 24 weeks
413		• Percent of eyes with worsening or improvement of diabetic retinopathy on clinical
414		exam
415		
416	I.	Main Safety Outcomes
417		Injected-related: endophthalmitis, retinal detachment, retinal tears, intraocular hemorrhage,
418		increased intraocular pressure
419		1
		Ocular drug-related: inflammation, increased intraocular pressure, need for ocular anti-
420		hypertensive, glaucoma surgery, or other IOP-lowering procedures, development or
421		worsening of cataract and cataract extraction, intraocular hemorrhage, migration of
422		dexamethasone to the anterior chamber and subsequent corneal complications
423		Systemic drug-related: Deaths, participants with at least one hospitialization, participants
424		with at least one SAE, and cardiovascular events, and cerebrovascular events as defined by
425		Antiplatelet Trialists' Collaboration

426

427 J. Schedule of Study Visits and Examination Procedures

428

Visit	Enroll in Run-In	Run-In Visits*	Randomization 0	4w-24w**
Visit Window		(+/- 1w)		(+/- 1w)
E-ETDRS best corrected visual acuity ^a	Х	Х	Х	Х
OCT ^b	Х	Х	Х	Х
Eye exam ^c	Х	Х	Х	Х
Blood pressure	Х		Х	
HbA1c ^d			Х	

* Visits at 4 and 8 (\pm 1) weeks during the run-in phase. Randomization visit (0) occurs at 12 (\pm 1) weeks from enrollment.

**Visits every 4 (±1) weeks post-randomization.

a= both eyes at each visit; includes protocol refraction in study eye at each visit and the non-study eye at the randomization visit and 24 week visit. E-ETDRS refers to electronic ETDRS testing using the Electronic Visual Acuity Tester that has been validated against 4-meter chart ETDRS testing.

b=study eye

c=both eyes at enrollment and randomization and study eye only at each follow-up visit. Includes slit lamp exam (including assessment of lens), measurement of intraocular pressure, and dilated ophthalmoscopy.

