1147 The 0.7 mg dexamethasone implant (Ozurdex) generally appeared to be safe and well-tolerated in phase III studies in which it was evaluated as treatment for macular edema secondary to retinal 1148 1149 vein occlusion.⁴² No cases of endophthalmitis occurred in these studies which included 1,256 1150 study participants followed for 12 months after enrollment. The 12-month incidence of 1151 subconjunctival hemorrhage ranged from 22.3%-24.9% in study eyes, some of which received 1 1152 and some of which received 2 implants at either the 0.7 mg or 0.35 mg dose. Cataract 1153 progression occurred in 29.8% of phakic eyes that received two 0.7 mg implants versus only 1154 5.7% of sham-treated phakic eves. An increase in IOP of 10 mmHg or more was observed in 1155 eyes that received two 0.7 mg implants at rates of 12.6% after the first implant and 15.4% after the second treatment. A total of 32.8% of study eyes receiving two 0.7 mg implants had at least a 1156 1157 10 mmHg increase in IOP from baseline during the 12 months of follow-up. Of eyes that 1158 received a 0.7 mg implant at baseline, 25.5% were started on an IOP-lowering medication during the first 180 days of the study. When a single 0.7 mg dexamethasone implant was administered 1159 in 55 vitrectomized eyes with DME,⁴⁴ the most common adverse events were conjunctival 1160 1161 hemorrhage (52.7%), conjunctival hyperemia (20.0%), eye pain (16.4%), increased IOP (16.4%), conjunctival edema (12.7%), and vitreous hemorrhage (10.9%). Of the 48 study participants 1162 1163 who were not on IOP-lowering medication at baseline, 8 (17%) began on IOP-lowering medication during the study. Additional adverse events that occurred in more than 5% but less 1164 than 10% of eyes were maculopathy (either epiretinal membrane or macular thickening), anterior 1165 chamber cells, foreign body sensation, iritis, and floaters. Migration of Ozurdex to the anterior 1166 1167 chamber with subsequent corneal edema is a rare complication of Ozurdex injections. This risk is associated with with aphakic eyes, ⁵⁰⁻⁵² and pseudophakic eyes with anterior chamber intraocular 1168 lens and iridectomy or disruption of the posterior capsule.⁵³⁻⁵⁵ In one study of 342 eyes with 1169

- 1170 macular edema due to retinal vein occlusion treated with Ozurdex, two eyes (~0.5%) had
- 1171 Ozurdex dislocated to the anterior chamber requiring surgical repositioning in the vitreous

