
1338

1339 7.4.1 Secondary Outcomes Analysis

1340 Analyses of secondary outcomes will be conducted as follows:

1341 Binary outcomes will be analyzed using logistic regression to control for baseline level of the

1342 outcome. Continuous outcome comparisons will be performed using ANCOVA with adjustment

1343 for baseline values. All linear model assumptions will be verified including linearity, normality

- 1344 of residuals, and homoscedasticity. If model assumptions are not met, a nonparametric analogue
- 1345 for ANCOVA will be considered. Multple imputation method will be implemented for missing 1346 data. GEE will be used to adjust for correlation between eyes of participants with two study
- 1347 eyes.
- 1348
- 1349

1350 7.5 Safety Analysis Plan

1351 Adverse events will be categorized as study eye, non-study eye, and systemic. The events will be tabulated and compared between treatment groups. Separate analyses will compare related adverse 1352

- 1353 events between groups.
- 1354
- 1355 Specific adverse events of interest will include:
- 1356 Injected-related: increased intraocular pressure, endophthalmitis, retinal detachment, retinal tears, intraocular hemorrhage 1357
- Ocular drug-related: increased intraocular pressure, need for ocular anti-hypertensives, 1358
- 1359 glaucoma surgery or other IOP-lowering procedures, development or worsening of cataract 1360 and cataract extraction, intraocular hemorrhage, inflammation, migration of Ozurdex to the anterior chamber and subsequent corneal complications 1361

1362 Systemic drug-related: Deaths, participants with at least one hospitialization, participants

with at least one SAE, and cardiovascular events and cerebrovascular events as defined by 1363 Antiplatelet Trialists' Collaboration 1364

1365 1366 • Systemic adverse events for participants with two study eves will be evaluated separately from participants with one study eye.

- 1367
- 1368

1369 Further definitions of the events for analysis and the analytic approach will be provided in the 1370 detailed statistical analysis plan.

1371 1372

1373 7.6 Additional Analysis Objectives Related to Design of Phase III Trial

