- Report the observed No. (%) by treatment group, adjusted difference in proportions, 95% confidence interval, and *P*value from treatment group comparisons
- AUC outcome: Mimic the linear mixed effect model in the primary analysis limiting the cohort to 24-week completers. No imputation will be performed.
 - Report mean ± SD and median [IQR] by treatment group, adjusted mean difference, 95% confidence interval, and *P*-value from treatment group comparison.
- 6. Summarize safety events occurred at any time during randomization phase
 - a. Ocular adverse events [eTable 5]
 - i. Tabulate No. (%) of eyes experienced at least one event by treatment group using *eyesRand* dataset
 - At least one ocular adverse events in the study eye
 - Increased intraocular pressure (IOP) events (a composite outcome, defined as any of the below). Each component will also be reported separately.
 - IOP increased \geq 10 mmHg from randomization at any visit
 - \circ IOP \geq 30 mmHg at any visit
 - Received ocular anti-hypertensives
 - Endophthalmitis
 - Inflammation
 - Any retinal detachment (a composite outcome, defined as any of the below). Each component will also be reported separately.
 - Traction retinal detachment
 - Rhegmatogenous retinal detachment
 - Unspecified retinal detachment
 - Retinal tears

- Retinal hemorrhage
- Vitreous hemorrhage
- Cataract extractions
- Glaucoma surgery
- Received post-injection treatment to lower IOP
- Migration of dexamethasone implant to the anterior chamber and subsequent corneal complications (combination group only)
 - Note: There is no specific MedDRA term for this type of adverse event. Instead, perform a manual check by searching for keywords "migration" and "anterior chamber" in the description field on the AE form, limiting to records in randomized eyes at post randomization.
- ii. Compare the frequency between treatment groups using Fisher's exact test and report *P*-value.
- iii. Footnote No. of patients experienced multiple types of ocular adverse events as listed above (if any)
- b. Systemic adverse events
 - i. All systemic adverse events will be reported by treatment group: combination group (unilateral participants), ranibizumab group (unilateral participants), and bilateral participants.
 - ii. Reduce *eyesRand* dataset to patient-level as a temporary dataset *ptRand*
 - iii. Tabulate No. (%) of participants experienced at least one event [eTable 6]
 - At least one systemic adverse event

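### The manuscript's ocular safety table (eTable 5) has no row for new or worsening cataract, a safety outcome that the protocol names in addition to cataract extraction

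*SAP*

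**What the plan says.** Protocol 1.3.I (Main Safety Outcomes) lists, as ocular drug-related outcomes, the development or "worsening of cataract and cataract extraction, intraocular hemorrhage, migration of" the implant. Protocol 7.5 (Safety Analysis Plan) repeats the item among the specific adverse events of interest: "glaucoma surgery or other IOP-lowering procedures, development or worsening of cataract", followed by extraction. The same section states "The events will be tabulated and compared between treatment groups". It then adds "Further definitions of the events for analysis and the analytic approach will be provided in the" detailed statistical analysis plan.

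SAP item 6.a.i sets out the rows of eTable 5, by number and percentage of eyes. The only lens row is "Cataract extractions". The general row is "At least one ocular adverse events in the study eye". Item 6.a.ii applies one test throughout: "Compare the frequency between treatment groups using Fisher"'s exact test, with a P-value.

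On the risk itself, protocol 6.5.1.2 reports from the retinal vein occlusion studies that cataract "progression occurred in 29.8% of phakic eyes that received two 0.7 mg implants versus only" 5.7% of sham-treated phakic eyes.

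**The concern.** Development or worsening of a cataract and its surgical removal are different events, and the second comes later. The protocol commits to both; the manuscript plan itemises only the second. Extraction is a weak stand-in in this trial. Eyes expected to need cataract extraction during follow-up are excluded (protocol 2.2.2, criterion p), and follow-up after randomization is 24 weeks. The extraction row could be close to zero in both groups while cataract progression differs.

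Assessing the safety of the combination is a stated objective (protocol 1.2), and the trial is meant to inform a phase III decision. Protocol 1.1.5 links cataract development to corticosteroid use. It does not expect this to affect the 6-month efficacy outcome, but the protocol still names cataract as a safety outcome. Under the plan as written, a reader of the primary paper would see no count for it.

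**Working it through.** No figure in the plan is in dispute, so the main check compares the two lists.

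| Ocular event in protocol 7.5 | Row in SAP 6.a.i (eTable 5) |
|---|---|
| Increased IOP; need for anti-hypertensives | IOP composite and its three components |
| Glaucoma surgery or other procedures to lower IOP | Glaucoma surgery; post-injection treatment to lower IOP |
| Endophthalmitis | Endophthalmitis |
| Inflammation | Inflammation |
| Retinal detachment, retinal tears | Detachment composite and components; tears |
| Intraocular hemorrhage | Retinal hemorrhage; vitreous hemorrhage |
| Implant migration | Migration, found by keyword search because it has no MedDRA term |
| Cataract extraction | Cataract extractions |
| New or worsening cataract | None |

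Other planned items that might fill the gap do not:

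- The any-ocular-event row pools cataract with everything else.
- eTable 7 (SAP 6.b.v) counts participants by MedDRA system organ class under systemic events, and cannot isolate cataract.
- The lens-status items in SAP 4 and 5 are a review of eyes whose acuity changed, a post hoc adjustment and baseline subgroups. None counts incident or worsened cataract.
- DSMC adverse event reports (protocol 7.8) are not manuscript reporting.

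**Size, for illustration.** Inputs from the protocol: 75 eyes per group (7.1); 29.8% versus 5.7% of phakic eyes (6.5.1.2). Assumptions, because the documents give no figure: the phakic share *f* (40%, 50% or 70%) and the fraction of the 12-month vein-occlusion rates reached by 24 weeks (one half or one quarter).

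Phakic eyes per group: 75 × *f* = 30, 37.5 (38 for the test) and 52.5 (52 for the test).

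Expected eyes with an event: 75 × *f* × rate.

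- Half rates, 14.9% versus 2.85%, *f* = 0.5: 37.5 × 0.149 = 5.6 versus 37.5 × 0.0285 = 1.1. Across *f*: 4.5 versus 0.9 up to 7.8 versus 1.5.
- Quarter rates, 7.45% versus 1.425%, *f* = 0.5: 2.8 versus 0.5. Across *f*: 2.2 versus 0.4 up to 3.9 versus 0.7.

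Precision at half rates: the difference is 14.9 − 2.85 = 12.05, about 12 points. The Wald 95% half-width at *n* = 38 is 1.96 × √(0.149 × 0.851/38 + 0.0285 × 0.9715/38) = 1.96 × 0.0638 = 12.5 points. It is 14.1 points at *n* = 30 and 10.7 at *n* = 52.

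Power: the exact binomial probability of all tables with two-sided Fisher p < 0.05.

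| Phakic eyes per group | Half rates | Quarter rates |
|---|---|---|
| 30 | 15% | 1% |
| 38 | 26% | 4% |
| 52 | 44% | 10% |

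At the full 12-month rates, which are probably too high for 24 weeks, 38 eyes per group give about 11.3 versus 2.2 events and 75% power.

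With 38 eyes per group, significance needs at least 6 versus 0 (p = 0.025) or 8 versus 1 (p = 0.028). Tables of 5 versus 0 (p = 0.054) and 7 versus 1 (p = 0.056) fall short. Between-eye correlation is ignored, as in the planned Fisher test.

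**The case against.** The strongest objection is about reach. The SAP Overview describes a plan for one manuscript and points to a separate protocol SAP. Protocol 7.5 leaves event definitions and the analytic approach to that detailed document. A promise to tabulate events is not a promise that each appears in one table of one paper. This stands as a limit: the documents do not show that cataract is missing from the trial's whole safety analysis. It does not restore the row, because the eTable 5 list is complete as printed.

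Second, the protocol joins development, worsening and extraction in one list entry, and it gives no scale for worsening. Keeping only the surgical event could be defended as keeping what is well defined. But the protocol names both, and reported adverse events are coded in MedDRA (protocol 6.2), so a count needs no grading scale.

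Third, the power figures rest on assumed inputs, and the cited rates come from another disease over a longer period. That is right, and the case for the row does not depend on them. Low power is no reason to omit it: the plan tabulates other rare events, such as endophthalmitis.

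Fourth, a phakic denominator departs from the all-eyes counts in 6.a.i, and it would be chosen after the 21 September 2017 database named in the SAP. The timing is a fair point for disclosure. The denominator itself is clinically required: a pseudophakic eye cannot develop cataract, and aphakic eyes are excluded. Investigators are not masked (protocol 1.4), so reporting bias is possible and should be stated.

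**Conclusion.** The point holds. Followed as written, the manuscript plan leaves a steroid risk named in the protocol out of its itemised safety tables; extraction alone does not represent it, and no other planned item counts it. This should be corrected, though it does not touch the primary efficacy result. At half the cited rates, and with 40% to 70% of eyes phakic, the row would hold roughly 4.5 to 7.8 events against 0.9 to 1.5, with Fisher power of 15% to 44%. At a quarter of the rates power is 1% to 10%. Its value lies in showing the counts, not in the test. Confidence is high for the table's contents; nothing is claimed about the detailed SAP, which was not available.

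**What to change.** In SAP 6.a.i, keep the extraction row and add to eTable 5:

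> New or worsening cataract (reported adverse events): No. (%) of eyes phakic at randomization with one or more MedDRA-coded cataract adverse events in the study eye reported after randomization, by treatment group.

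Apply the Fisher test already planned in 6.a.ii, and add a footnote:

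> Investigators knew the treatment assignment, and 24 weeks of follow-up gives limited power for this event.

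Record that the row was added to this plan to match protocol 7.5. Do not derive it from the lens assessments at visits, because the protocol gives no threshold for worsening.

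The cost is one row and one footnote, from adverse event reports that are already coded and a baseline lens-status variable that the plan already uses. The drawbacks are possible ascertainment bias from unmasked reporting and a weak test. No sample size, power or alpha figure in the plan changes.

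### The search for implant migration does not say whether one or both keywords must appear, and its two terms are too narrow under either reading

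*SAP*

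**What the plan says.** Protocol section 1.3 (I), Main Safety Outcomes, and section 7.5, Safety Analysis Plan, both list this event among the ocular drug-related outcomes. Section 7.5 words it as "migration of Ozurdex to the anterior chamber and subsequent corneal complications". The assessment of safety of the combination is one of the stated study objectives (section 1.2).

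The SAP, item 6.a (Ocular adverse events, eTable 5), gives the event its own row, for the combination group only. A note under the row explains how cases are found: "There is no specific MedDRA term for this type of adverse event". It continues: "Instead, perform a manual check by searching for keywords". The keywords are 'migration' and 'anterior chamber'. They are sought in the description field of the adverse event form, among post-randomization records of randomized eyes.

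Protocol section 6.5.1.2 describes the same event in other words. In a series of 342 eyes with retinal vein occlusion, two eyes had "Ozurdex dislocated to the anterior chamber requiring surgical repositioning in the vitreous" cavity.

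**The concern.** The note leaves two things open. It joins the keywords with 'and' without saying whether a record must contain both or only one. It also lists only two exact expressions, although sites write free text and this event can be described in several ways: as a verb ('migrated'), with another word ('dislocated', 'displaced'), or with 'AC' for anterior chamber.

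The event is rare, so the row will probably read zero or one. With so small a count, a single record that escapes the search decides whether the plan reports that migration was seen or that it was not. The documents treat migration as serious enough to name it as a main safety outcome, and the two cited cases needed surgical repositioning. A reported zero is useful for planning phase III only if the search could have found a case.

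**Working it through.** The plan states no figure for this point, so there is nothing to reproduce. The check has two parts.

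**1. What the two keywords retrieve.** Literal matching, ignoring case, under both readings. Apart from the protocol wording in the second row, the descriptions are illustrations.

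| Description | Both required | Either enough |
|---|---|---|
| migration of implant to the anterior chamber, corneal edema | found | found |
| "Ozurdex dislocated to the anterior chamber requiring surgical repositioning in the vitreous" (protocol 6.5.1.2) | missed | found |
| implant migrated to the anterior chamber | missed | found |
| migration of implant into AC | missed | found |
| implant migrated into AC | missed | missed |
| implant dislocated into AC | missed | missed |
| implant in AC | missed | missed |
| implant displaced, corneal edema | missed | missed |

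'Migrated' does not contain 'migration', and 'AC' does not match 'anterior chamber'. The choice between the two readings decides rows two to four. The last four rows are missed under either reading.

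**2. What one missed record would do.**

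Inputs:
- Rate: 2 of 342 eyes (protocol 6.5.1.2, which rounds it to about 0.5%).
- Combination-group eyes: 75 planned (protocol 7.1).

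Exact rate:
- 2/342 = 0.585% per eye.
- Expected events: 75 × 0.00585 = 0.44.
- Chance of at least one: 1 − (1 − 0.00585)^75 = 0.356, or 36%.

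Rate as rounded in the protocol:
- Expected events: 75 × 0.005 = 0.375.
- Chance of at least one: 1 − 0.995^75 = 0.313, or 31%.

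One event missed changes the row from 1/75 = 1.3% to 0.

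The documents do not say how often a site's wording would escape the search. Assume, for illustration, that one third to one half of events would:
- One third missed: 1 − (1 − 0.00585 × 2/3)^75 = 0.254.
- One half missed: 1 − (1 − 0.00585 × 1/2)^75 = 0.197.

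The chance that the row shows at least one case then falls from 36% to between 25% and 20%. Put differently, the chance that an event occurs and the row still reads zero is 0.356 − 0.254 = 0.10 to 0.356 − 0.197 = 0.16.

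**The case against.** The note calls for a manual check. A sensible analyst would probably treat either keyword as enough and would recognise variants in the records being read. A reader might infer that the search is bound to miss the protocol's own example, or any record that says 'migrated' or 'dislocated'. The documents do not support that: under the either-keyword reading, any description that spells out 'anterior chamber' is found. What remains is that the rule is unstated, and that reading the retrieved records cannot recover those never retrieved.

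The trial also has other safeguards. Study eyes have a slit lamp examination at every follow-up visit (protocol 4.7), the Coordinating Center verifies the coding and reporting of adverse events (6.2), and the DSMC reviews cumulative events semi-annually (6.4). A reader might infer that a missed case would vanish from the safety data. It would not: it would still count in the eTable 5 row for at least one ocular adverse event. These safeguards do not fill the migration row, however. By the SAP's own account no specific code exists, so verified coding does not single out the event.

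It may also seem that corneal complications go unsearched and need a row of their own. The outcome is corneal complications subsequent to migration, so finding the migration leads to them. A separate row is a matter of preference.

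Finally, the rate is borrowed. It comes from eyes with vein occlusion, and protocol 6.5.1.2 links the risk to aphakia, anterior-chamber lenses and posterior capsule disruption. Section 2.2.2 excludes aphakia, anterior-chamber lenses, and sutured lenses with a ruptured capsule. A reader might instead double the expected count by allowing two implants per eye. That is not supported either: the cited rate is per eye, and the second implant depends on the retreatment criteria (section 4.8).

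**Conclusion.** The point holds as a minor improvement to case finding. The stated search has no rule for combining its keywords. If both are required, it misses the protocol's own wording. If either is enough, it still misses descriptions that contain neither exact expression. At 2/342 per eye and 75 eyes, there are 0.44 expected events and a 36% chance of at least one, so one missed record could be the difference between 1/75 and zero.

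This rests on three assumptions: that the cited rate carries over, although it is illustrative and probably high for this population; that the planned 75 eyes are the denominator; and that matching is literal, as keyword searching suggests. The examples missed under both readings are plausible wordings, not records known to exist.

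The conclusion concerns only the documents at hand. The SAP reviewed is a technical plan for the primary manuscript. Its overview points to a separate statistical analysis plan, which may define the event further.

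**What to change.** Replace the note in SAP item 6.a with a rule on these lines:

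- Search post-randomization study-eye adverse event descriptions for migrat\*, dislocat\*, displac\*, 'anterior chamber', 'AC' and cornea\*. Any one term is enough.
- Match 'AC' as a whole word, because as a bare string it also hits 'macular' and 'cataract'.
- Existing Coordinating Center staff read the retrieved descriptions and confirm cases. Alternatively, they read all study-eye descriptions from dexamethasone-treated eyes, about 75 eyes as planned.
- Count a corneal event in this row only when it follows migration.

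Every description in the table above is retrieved by this list. The cost is a change of wording and a short extra read, with some false hits to discard, mainly from 'anterior chamber' and cornea\*. No new data, visits or modelling are needed.
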